## **EXPERIMENTAL PROTOCOL**

Each participant will participate in two study visits, one consent/pre-scan visit and one scanning visit within 3 days apart. During the consent/pre-scan visit, participants will undergo consent for participation in the study and Quantitative Sensory Testing (QST). During the scanning visit, simultaneous fMRI/EEG data will be acquired while participating in additional tasks and administration of nitrous oxide gas.

### **Consent/Pre-Scan Visit**

The study coordinator will determine whether the volunteer meets inclusion and does not meet exclusion criteria prior to consent. Following consent, each volunteer will complete a resting state questionnaire and QST familiarization/training during EEG acquisition. MR-compatible EEG cap and electrodes will be affixed to the participant's scalp to monitor brain activity during QST training. QST will consist of a constant pressure applied to the lower leg and/or visual stimulus outside of the scanner. Following each stimulus, participants will rate the pain intensity (0 = "no pain, 100 = "worst pain imaginable") and pain unpleasantness (0 = "neutral", 100 = "extremely unpleasant"). Participants will be

asked to complete another resting state questionnaire following training on simultaneous visual stimulus and pressure cuff. During this visit, participants will also be seen briefly by an anesthesiologist for an airway assessment to check for eligible Mallampati 1 or 2 airways.

Scanning Visit

Simultaneous Functional Magnetic Resonance Imaging/Electroencephalogram (fMRI/EEG)

Each volunteer will participate in one scanning visit in which simultaneous fMRI/EEG data will be collected wherein they receive placebo (20 minutes) followed by inhaled nitrous oxide at analgesic levels (35% inhaled concentration) over 40 minutes, then a nitrous oxide dose consistent with anesthetic-induced unconsciousness (70%) for 15 minutes [See Figure 1];

[figure not shown]

Figure 1. Study design schematic

Upon arrival, participants will complete baseline questionnaires (Part 1a). Prior to drug exposure, volunteers will be given an altered states of consciousness (ASC) questionnaire followed by a baseline resting state fMRI scan. During the placebo period, fMRI data will be acquired during additional tasks: visual stimulation task, evoked pressure pain applied to the lower leg induced by a cuff/automated tourniquet, and a combination visual stimulation and pressure pain cuff task. These scans will be repeated during both analgesic and anesthetic doses of nitrous oxide. End-tidal nitrous oxide concentrations will be assessed by standard gas analyzers during spontaneous ventilation through a secured face mask with tight seal.

All subjects will have MR-compatible EEG electrodes affixed to their scalp for monitoring during the study. Participants will first complete an altered states of consciousness questionnaire. Continuous EEG will be acquired during a baseline (rest) period followed by three additional tasks mentioned previously.

For each participant, these tasks will be repeated at a low dose of nitrous oxide that is normally associated with analgesia (35% inhaled concentration) and a higher dose of nitrous oxide that is associated with anesthesia. Following administration of the analgesic dose of nitrous oxide, participants will be asked to complete a questionnaire to assess altered states of consciousness. Each testing session will conclude with a 15-minute continuous EEG acquired during the participant's recovery of consciousness. Following testing, the participants will be asked to complete an altered state of consciousness questionnaire.

To maximize safety, nitrous oxide will be delivered using MRI-compatible anesthesia machines at the University of Michigan hospital, and anesthetic doses of nitrous oxide will be administered outside of the scanner, where airway patency and physiological stability will be established prior to imaging the state of anesthetic-induced unconsciousness. At least two fully-trained anesthesiologists will direct all anesthetic administration. In order to maximize clinical monitoring during emergence, recovery from anesthetic doses will occur outside of the MRI scanner as well. All participants will receive ondansetron (4mg IV) with an additional dose of dexamethasone (4mg IV) if needed to prevent nausea and vomiting. In addition, glycopyrrolate (0.42-0.4 mg IV), labetalol (5-10 mg/kg IV), and midazolam (1-2 mg IV) will be available for use to mitigate any side effects, as needed. Also, standard intraoperative monitors (electrocardiogram, pulse oximetry, capnography) will be used.

Subjects will only be discharged if standard clinical criteria for discharge at UMHS is met. This includes being awake, fully responsive, able to walk, able to urinate, and no significant nausea and vomiting. The medication will be given as needed during the recovery period while being monitored by [name] or another fully trained anesthesiologist. Participants will not be allowed to drive home and transportation will be provided. In addition, approximately 24 hours after the nitrous anesthetic, the study coordinator will call the participant to follow-up and ensure that there are no adverse events. If an adverse event is detected, the study coordinator will immediately contact [name] and determine the appropriate course of actions to be taken.

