## METHODOLOGY

Here we describe a mechanistic study in healthy human volunteers to achieve the objectives of our specific aims.

*Participant Recruitment:* We will recruit 25 individuals for an fMRI/EEG study.

Healthy volunteers will be identified through the UM Clinical Studies website (<http://www.umclinicalstudies.org>) for research volunteers. We will also utilize the Minority Health Research Program (MHRP) to help recruit minorities into our study. Our goal is to recruit groups of subjects that are representative of the southeastern Michigan population. (See Appendix A for ethnic and racial targeted enrollment). All interested volunteers will first contact [name] or the study coordinator for a preliminary screen to determine if the subject meets the inclusion/exclusion criteria and that the subject understands the research study. Specifically, the screening script will be read to potential participants, after which, they will be screened over the phone for eligibility using phone screening questionnaires. All screening documents have been attached to the Subject Recruitment section of the IRB application. [name] or the study coordinator will also answer any questions that the potential participants may have at this time. If the potential participant responds to the psychosis, the mood disorder, or the Patient Health Questionnaire-9 (PHQ-9) depression screening questionnaire in

a manner that would potentially indicate a depressive/mood diagnosis, he/she will be referred to the Depression Center at the University of Michigan Health System ([name]). Eligible participants will then be scheduled to participate. [name] and the study coordinator are responsible for obtaining full written informed consent on the day of the first study visit upon the participant's arrival. Privacy will be maintained throughout the screening process per normal UMHS HIPAA privacy policies.

Study participants:

*Inclusion criteria* include: age 21-40, right-handed, American Society of Anesthesiologists Class 1 physical status, body mass index <30, with Mallampati 1 or 2 airways.

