*Exclusion criteria* include: history of obstructive sleep apnea, history of difficult airway with previous anesthetics, gastroesophageal reflux, hypertension or other cardiovascular abnormalities, pulmonary hypertension, history of drug use, history of chronic alcohol abuse, history of pain disorders, history of depression, psychosis or bipolar disorder, history of seizures or other neurologic disorders, history of methylenetetrahydrofolate reductase deficiency (a contraindication for nitrous oxide), history of known hypersensitivity to midazolam, Zofran, labetalol or glycopyrrolate, pregnant and / or nursing mothers, contraindications to the neuroimaging methods used (i.e. metal implants), tattoos in the head/neck region (all other tattoos may be subject to study exclusion by investigators), and any impairment, activity, or situation – as determined by the study coordinator or primary investigators – that would prevent satisfactory completion of the study protocol.

*Power analysis:* We calculated power using data from fMRI analyses. Based on an effect size (Cohen's *d*) derived from preliminary data, 22 participants are required for a 90% power to detect a statistically significant reduction in average path length (reflecting network efficiency). In case of drop out across, we will continue to recruit until we have 22 volunteers with completed data sets.

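### The as-needed labetalol dose is printed per kilogram, unlike the other four IV drugs, and the glycopyrrolate range beside it runs backwards

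*Combined protocol and SAP*

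**What the plan says.** The medication paragraph in the Scanning Visit part of the Experimental Protocol names five IV drugs. For nausea, the plan gives "ondansetron (4mg IV) with an additional dose of dexamethasone (4mg IV) if needed to prevent nausea and vomiting". For other side effects, "glycopyrrolate (0.42-0.4 mg IV), labetalol (5-10 mg/kg IV), and midazolam (1-2 mg IV) will be available for use to mitigate any side effects".

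Labetalol appears in one other place, the exclusion criteria under Methodology, which list "history of known hypersensitivity to midazolam, Zofran, labetalol or glycopyrrolate". That entry carries no dose.

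On supervision, the same Scanning Visit text says "At least two fully-trained anesthesiologists will direct all anesthetic administration". The discharge paragraph that follows adds "The medication will be given as needed during the recovery period while being monitored by" an anesthesiologist.

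**The concern.** A single weight-based entry is not an error in itself, since different drugs can be dosed in different units. Three features together make this one doubtful:

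- It stands alone among five drugs in one paragraph.
- The entry next to it cannot be right as printed, because its lower limit exceeds its upper limit.
- The plan gives no maximum dose, titration rule or drug-specific trigger against which the labetalol figure could be checked. The printed dose is the only limit the protocol sets.

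At stake are safety and protocol compliance in healthy volunteers. If a flat dose was meant, a clinician who gives 5-10 mg departs from the written protocol, and one who follows the protocol gives hundreds of milligrams. If the per-kilogram dose was meant, it differs enough from its neighbours to need explicit confirmation.

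**Working it through.** The plan shows no calculation behind these doses, so there is no derivation to reproduce. The check compares units and range order, then sizes the gap between the printed labetalol dose and the same figures read as flat milligrams.

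**Inputs from the plan (Scanning Visit text)**

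| Drug | Printed IV dose | Unit | Range order |
|---|---|---|---|
| Ondansetron | 4 | mg | single value |
| Dexamethasone | 4 | mg | single value |
| Glycopyrrolate | 0.42-0.4 | mg | descending |
| Labetalol | 5-10 | mg/kg | ascending |
| Midazolam | 1-2 | mg | ascending |

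**Unit.** Four of the five entries are flat milligram doses. Only "labetalol (5-10 mg/kg IV") is per kilogram.

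**Range order.** For "glycopyrrolate (0.42-0.4 mg IV"), 0.42 > 0.4, so the first limit exceeds the second by (0.42 - 0.4)/0.4 = 5%.

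**Labetalol as printed.** Total dose = dose per kg × body weight. The plan gives no body weights, so those below are assumptions.

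| Assumed weight | 5 mg/kg | 10 mg/kg | Flat reading |
|---|---|---|---|
| 50 kg | 250 mg | 500 mg | 5-10 mg |
| 70 kg | 350 mg | 700 mg | 5-10 mg |
| 90 kg | 450 mg | 900 mg | 5-10 mg |

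These weights are compatible with the inclusion limit ("body mass index <30") at assumed heights of 1.60, 1.70 and 1.80 m: 50/1.60² = 19.5, 70/1.70² = 24.2 and 90/1.80² = 27.8. The limit does not itself bound weight, because the plan gives no heights.

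**Does the result depend on the assumed weights?** The lowest literal dose equals the highest flat dose when 5 mg/kg × weight = 10 mg, that is, at 10/5 = 2 kg. Above 2 kg the readings do not overlap, so the choice of adult weight does not matter.

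**Size of the gap.** Like for like (5 mg/kg against 5 mg, or 10 mg/kg against 10 mg), the ratio equals body weight in kg: 50-fold at 50 kg and 90-fold at 90 kg. The smallest gap at 50 kg, lowest literal against highest flat dose, is 250/10 = 25-fold.

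**The case against.** The strongest reply is that the plan does not contradict itself: labetalol has one stated dose, in one place. The 5-10 mg figure is inferred from the neighbouring entries, and showing that the printed dose is wrong would need a reference dose that the plan does not contain. This stands as a limit on the claim. What is established is that the entry is anomalous and unresolved, not which dose was intended.

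The text was also read from PDF by a program, and a misread digit in the glycopyrrolate range cannot be excluded. That weakens the descending range as corroboration. It is less persuasive for labetalol, because an extraction fault is unlikely to add a per-kilogram unit to just one of five entries. Checking the source file would settle both.

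Finally, the practical risk is limited. The drug is held for contingent use, and participants are ASA class 1 with hypertension and other cardiovascular disease excluded. ECG, oximetry and capnography are in place, and anesthesiologists direct administration and watch recovery. Nothing suggests that a non-specialist would dose from this sentence. All of that is fair and makes harm from literal compliance unlikely. But if the flat dose was intended, the safeguard works only because clinicians would disregard the written instruction.

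**Conclusion.** The concern holds. Labetalol is the only per-kilogram entry among five IV drugs, the adjacent glycopyrrolate range descends as printed, and nothing elsewhere in the document resolves either. The literal and flat readings of the labetalol dose differ at least 25-fold at an assumed 50 kg and by more at higher weights. That they do not overlap holds for any weight above 2 kg and so rests on no weight assumption.

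Two things remain open: the intended labetalol unit and the intended glycopyrrolate limits. Reading labetalol as 5-10 mg is an inference from its neighbours. This is an operative dosing instruction for healthy volunteers, so it should be fixed, although supervision and as-needed use keep the practical risk low. No endpoint, power calculation or analysis is touched.

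**What to change.** 1. Check both entries against the source file, to rule out a reading error.
2. Have the responsible anesthesiologist verify the labetalol unit. Amend the sentence to 5-10 mg IV if the per-kilogram unit is confirmed as an error. Otherwise, state the confirmed per-kilogram dose explicitly.
3. In the same amendment, confirm the glycopyrrolate limits and print them in ascending order. The intended lower limit cannot be derived from the document and should not be guessed.

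The cost is a one-sentence protocol correction, with no effect on design, sample size or analysis.

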## **DATA COLLECTION**

Resting State Functional Connectivity (fcMRI).

During fcMRI, participants will either be at rest or receiving a pain stimulus via a pressure cuff applied to the left lower leg evoking tonic pressure with pain of 40 on a 100-point numerical rating scale (See below; 0=no pain; 100=worst pain imaginable). Functional connectivity fMRI will be performed on a 3 Tesla Philips Achieva (Best, Netherlands) using a T2\* weighted echo-planar sequence with the following parameters: TR/TE = 2000/30ms, flip angle=90°, FoV = 200x200mm, 48 AC-PC aligned slices, slice thickness 3 mm, scan time = 6min. These data will be analyzed using two approaches: a model-free independent component analysis (ICA) and seed-voxel based method (from evoked pain fMRI; See below).

Evoked pressure pain with blood pressure cuff:

Calibrated cuff pain stimuli will be delivered to the gastrocnemius area of the dominant leg using a validated cuff pain device that has been recently adapted to the MRI scanning environment. A computer controlled air compressor (Hokanson Rapid Cuff Inflator) will inflate the cuff to a pre-specified pressure, and maintain the pressure at that level. Subjects will participate in one test session of cuff pain prior to the EEG and the fMRI session. Pressure pain will be applied for a continuous 6-minute period three times during the fMRI protocol to evaluate functional brain connectivity response to deep pain (see below). One advantage to using cuff algometry pain is that unlike more superficial methods (e.g. heat pain), cuff pain responses are unaffected by sensitization or desensitization of the skin, indicating that this procedure primarily assesses sensitivity in muscle and other deep tissues. We have considerable experience applying these techniques in both healthy adults and chronic functional pain patients, and have found that all subjects are able to tolerate these procedures without any lasting discomfort.

*Training Session.* A training session with the cuff will be used to familiarize subjects with the stimuli and rating procedures and determine appropriate stimulus intensities to be used subsequently in the imaging session (see below). This can take place on the day of fMRI or during the in-clinic consent visit. During training, subjects will be maintained in a seated position in a chair with the left foot resting on a support at a slightly elevated position (but at a lower level than that of the hips, in order to facilitate blood circulation in the leg).

Testing will begin with an ascending series of pressure stimuli starting at 60 mmHg and increasing 20 mmHg increments. Ten seconds after the end of each stimulus, subjects will complete two 0-100 numerical rating scales: pain intensity (0 = “no pain”, 100 = “worst pain imaginable/extreme pain”) and pain unpleasantness (0 = “neutral”, 100 = “extremely unpleasant”). The ascending series will end when a pain intensity rating of >70/100 is obtained. Participants may also receive a continuous tonic pressure for 6 minutes to their lower leg using the cuff, and asked to rate the intensity and unpleasantness of the stimulus at certain intervals during the test, up to three times. A short break will be given between each pressure test.

This training session will have the effect of rendering subjects non-naïve to the experimental conditions in the imaging session, an aspect that might be argued to have some impact on the imaging results (particularly with regard to brain activity underlying cognitive and emotional functions). However, the training session has several advantages that outweigh these concerns: (1) identification and exclusion of individuals with unstable ratings, (2) a thorough training in the use of the rating scales, and (3) the reduced potential for developing experiment-related anxiety and head motion in the imaging session.

*Imaging session.* On the day of the imaging session, the Pain0-Pain70 pressures will be briefly recalibrated prior to scanning using procedures similar to those used during the training session.

During the fMRI scan runs, subjects will receive cuff pressures calibrated to each subject’s Pain30-50 applied for a continuous 6-min period to evaluate functional brain connectivity response to tonic deep pain. Following each cuff pain run, participants will be asked to rate the degree of pain intensity and unpleasantness on a 100-point numerical rating scale.

### Visual Stimulation Task

During the visual stimulation, participations will be undergoing a 3-minute period of dynamic visual stimulation tasks which consists of alternating 20 second blocks of flashing (8 Hz frequency) blue-yellow annulus checkerboard and a static fixation cross. The checkboard will be presented at a fixed illumination level in within the range of 4.5 to 76 lux. Following stimulation, participants will be asked to rate the intensity and unpleasantness of the stimulus on a 100-point numerical rating scale.

### Electroencephalogram (EEG)

All subjects will have EEG electrodes affixed to their scalp for monitoring during the study. We will use the Brain Products MR-compatible EEG system for EEG, as it offers the capability to record 64 channels of EEG data in the MR environment. This equipment has been tested and approved for safe use by the University of Michigan Biomedical Engineering Department.

The EEG electrodes and the cap to hold the electrodes will be disinfected after each use with an FDA-approved solution provided by EGI Geodesic System (there is no standard UMHS protocol for this). The EEG electrodes have minimal risk but may cause a slight irritation to the skin that will resolve on its own. Acquisition of EEG data will occur during both the consent/QST visit and the fMRI scanner visit. During the QST visit, EEG data will be acquired during rest periods and stimulus presentation. During the scanner visit, EEG will be acquired simultaneous with the fMRI data. The sampling frequency at which data will be acquired is 5000 Hz and EEG data will undergo pre-processing prior to assessment of brain network dynamics.

### Questionnaire

Each participant will complete a series of questionnaires to further characterize the study participants on the day of testing prior, during and after the experiment. Before testing, participants will complete general psychometric surveys to assess personality, emotion (positive and negative affect), depression, anxiety and handedness. All surveys have been attached to the Survey Research section of the IRB application.

During the nitrous oxide protocol, the participants will complete four additional questionnaire components; an altered states of consciousness and resting state questionnaires, as well as intensity and unpleasantness rating. The altered state consciousness (ASC) questionnaire is a survey completed by the participant on a visual analog scale (0 – 10) to assess the affective experience of nitrous oxide administration during the study. The resting state questionnaire assess resting state cognition during non-sensory experiences (resting state scan), such as mind-wandering and self-referential thinking. Intensity and unpleasantness rating will mimic the quantitative sensory testing session, given prior to each experiment, where participants are asked to rate the intensity and unpleasantness of the sensory stimuli on the Gracely Box Scale, previously used in our lab.

The ASC questionnaire should take 10 minutes to complete and will be administered at baseline, and after the analgesic and anesthetic dose periods. The resting state questionnaire will be administered

following the resting state periods and stimulus periods during the consent/QST visit. Intensity and Unpleasantness ratings will be acquired during and following both resting scans and sensory stimuli scans (cuff pain and visual stimulation).

The final survey should take less than one hour, may be completed online and should be completed within 48 hours after the study visit. This survey will contain questionnaires related to altered states of consciousness and psychometrics.

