## STATISTICAL ANALYSIS

### Functional connectivity magnetic resonance imaging (fcMRI)

fcMRI will be performed as described in our previous publications. During fcMRI, participants will either be at rest or receiving a pain stimulus via a pressure cuff applied to the left lower leg evoking tonic pressure with pain of 40 on a 100 point numerical rating scale (0=no pain; 100=worst pain imaginable). This sustained pain is relevant to deep musculoskeletal clinical pain and can be applied for long durations (i.e. minutes) without tissue damage. Data will be corrected for physiological effects such as cardio-respiratory fluctuations that are known to influence fcMRI estimation. Resting connectivity network analysis will be performed using the FSL (FMRIB's Software Library, [www.fmrib.ox.ac.uk/fsl](http://www.fmrib.ox.ac.uk/fsl)) software package. All data will be corrected for motion artifacts, smoothed (FWHM 5 mm), and high-pass temporal filtered ( $f = 0.006\text{Hz}$ ). ICA Approach. The within- and between-subject resting fMRI data analysis will be performed using ICA through Multivariate Exploratory Linear Optimized Decomposition into Independent Components (MELODIC, an FSL tool) and a previously validated dual regression approach. We will apply probabilistic ICA to identify global, independent patterns of functional connectivity existent in the entire subject population. The number of independent components will be limited to 25 to reduce subcomponents. Networks of interest will be selected and the spatial independent component maps identified from the population data will be used as a spatial regressor in a general linear model of the subject's resting fcMRI data. This will allow us to estimate subject-specific spatial maps for each component. These maps will then be passed up to group analysis. Seed-voxel Approach: We will evaluate functional connectivity using seed-voxels from brain regions previously shown to be involved in consciousness or pain. The average time course in these regions will be used as regressors in a whole brain general linear model to find other brain regions also correlated with the seed region. A whole brain general linear model will be performed using the seed time course, averaged over a 3 mm radius sphere, as the regressor of interest. The resulting single subject maps will be normalized to standard space and passed up to group analyses. fcMRI group analyses: Nitrous oxide effects on brain connectivity will be estimated using a factorial model with treatment (nitrous versus placebo) and time (pre versus post) as factors. All statistical maps will be corrected for multiple comparisons on the cluster level  $p < 0.05$ , derived from an uncorrected  $p < 0.001$  on the voxel level.

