
### Network Analysis

In terms of network properties to be analyzed, the **degree** is the number of connections a node (in this case, a given brain region) has, while the **modularity** is a measure of the extent to which the connected regions form individual functional modules. We will first investigate the characteristic modules

corresponding to different states, then quantify the modularity of the networks. High-degree **hubs** facilitate “shortcuts” of network information transmission (much like a hub airport facilitates travel shortcuts) and are identified with the measures of *centrality* in a network. The centrality of a node measures its relative ability to integrate information globally within a brain network. We will assess several centrality measures (degree centrality, closeness centrality, betweenness centrality and Eigenvector centrality) to test the robustness of the hub structure. The **average path length**, which measures the mean number of steps along the shortest paths for all possible pairs of network nodes, will be used for quantifying the **global efficiency** of brain networks (since efficiency varies inversely with path length). Network measures will be compared across states (waking, analgesia, anesthesia) using a repeated measures two-way analysis of variance (ANOVA) and a post hoc Tukey multi-comparison test (behavioral state as the within-subjects factor, anesthetic agent as the between-subjects factor). A p value <0.05 will be considered significant.

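### The Questionnaire section places intensity and unpleasantness ratings inside the resting scans, which would make rest a task that varies with state; the sections on rating times need reconciling

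*Combined protocol and SAP*

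**What the plan says.** Four parts of the combined protocol and SAP bear on when ratings are taken.

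- **Questionnaire:** "Intensity and Unpleasantness ratings will be acquired during and following both resting scans and sensory stimuli scans". This is the only sentence that sets rating times for resting scans.
- **Data Collection, imaging session (cuff runs):** "Following each cuff pain run, participants will be asked to rate the degree of pain intensity and unpleasantness".
- **Visual Stimulation Task:** "Following stimulation, participants will be asked to rate the intensity and unpleasantness of the stimulus".
- **Statistical Analysis, fcMRI:** "During fcMRI, participants will either be at rest or receiving a pain stimulus via a pressure cuff". No rating task is part of either condition. On preprocessing it says: "All data will be corrected for motion artifacts, smoothed (FWHM 5 mm), and high-pass temporal filtered". It states no regressor for rating periods, no censoring of them and no rule for ratings that cannot be given.

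Two further passages set the comparison. The scanning-visit description gives 35% for 40 minutes and "then a nitrous oxide dose consistent with anesthetic-induced unconsciousness (70%) for 15 minutes", and says of the scans: "These scans will be repeated during both analgesic and anesthetic doses of nitrous oxide". The Network Analysis section says: "Network measures will be compared across states (waking, analgesia, anesthesia"), with behavioral state as the within-subjects factor.

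**The concern.** A rating needs attention, a judgement about sensation and a response. A run that contains ratings is therefore not a resting run in the sense the analysis assumes. Generic motion correction deals with some of the head movement a response may cause. It does not remove the brain activity evoked by judging and responding.

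If every state were contaminated equally, a within-person contrast would largely cancel the effect. Equality is unlikely here. A volunteer who is awake can answer, while one at a level described as consistent with unconsciousness is not expected to. Some of the difference between waking and 70% could then reflect the presence or absence of a rating task and not the drug. A larger sample would not average this out, because the bias has the same sign in every volunteer.

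What is at stake is the interpretation of resting connectivity. The plan's expected outcomes concern links between pain regions such as the insula and the default mode network, and a pain-type judgement made during the scan could plausibly affect those links.

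**Working it through.** **1. Rating times, by type of run**

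| Run | Questionnaire section | Run-specific section |
|---|---|---|
| Rest | during and after | none |
| Cuff | during and after | after (imaging session) |
| Visual | during and after | after (Visual Stimulation Task) |

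For cuff and visual runs two statements disagree. For rest there is one statement, and it includes in-run rating. The only other place that allows ratings at intervals within a tonic stimulus is the training session.

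**2. Direction of the artefact**

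Suppose in-run ratings lower modularity by an amount *c* that depends on state, with *c*(70%) < *c*(waking) because the unresponsive volunteer does not rate. With no drug effect:

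- 70% minus waking = *c*(waking) − *c*(70%) > 0, a spurious rise. The Expected Outcomes section predicts a rise at the higher dose.
- 35% minus waking = *c*(waking) − *c*(35%). This is zero if contamination at 35% equals that at waking, and positive if it is weaker. The plan predicts a fall at the lower dose, so here the artefact is neutral or works against the hypothesis.

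**3. Share of a run that ratings would occupy**

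The Data Collection section gives TR 2000 ms and 6 minutes, so a run has 360 s ÷ 2 s = 180 volumes. The number and length of in-run ratings are not given. If each takes 10 to 30 s (assumed):

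- one rating takes 5 to 15 volumes, or 2.8% to 8.3% of the run;
- three ratings take 15 to 45 volumes, or 8.3% to 25%.

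**4. Illustrative simulation**

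There were 300 runs with and without rating events. Only TR and run length come from the plan. Assumed: 90 nodes, 6 modules, 20% edge density, 16-second rating periods, and a common evoked response in 25% of nodes.

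| Rating periods | Amplitude | Mean correlation among responding nodes (0.14 without ratings) | Modularity shift |
|---|---|---|---|
| 3 | 0.5 SD | 0.16 | negligible |
| 3 | 1 SD | 0.21 | 0.600 to 0.592, about 0.6 SD |
| 6 | 1 SD | 0.26 | about 1.1 SD |

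Shifts are in SDs of the run-to-run difference. Average path length moved by at most 0.16 SD in any setting. Head motion was not simulated.

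**5. What a shift of a given size would do**

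For a two-sided paired t-test at 5% with n = 22 (the plan's number of completers), the critical value on 21 df is 2.080. A bias of *b* SDs of the within-person difference gives noncentrality *b*√22. With no drug effect, the test rejects as follows:

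| *b* | *b*√22 | Rejection rate |
|---|---|---|
| 0.1 | 0.469 | 7% |
| 0.2 | 0.938 | 15% |
| 0.3 | 1.407 | 27% |
| 0.5 | 2.345 | 61% |

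This table shows sensitivity to a bias of given size. It does not say which row applies. The simulation as described has no between-volunteer variation in drug response, so its standardised shifts may be too large to read straight into the table.

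The plan's own figure, 22 participants for 90% power on average path length, is not disputed. It cannot be reproduced because Cohen's *d* is not given. Back-solving a paired t-test at 5% gives *d* of about 0.73 two-sided or 0.65 one-sided.

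**The case against.** The strongest reply is that this turns on one word in a questionnaire paragraph. The same section describes these ratings as ratings of sensory stimuli, modelled on the sensory-testing session, and a resting scan has no stimulus. The run-specific sections rate afterwards, and the analysis section calls the condition rest. Loose drafting is at least as plausible as a planned in-run task. That is fair, and it is why the point is framed as an inconsistency. It does not dispose of the point, because no other sentence governs resting scans, and staff who follow the document as written would collect ratings in them. The link to the sensory-testing session also cuts the other way, since that training allows ratings during a tonic stimulus.

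Other parts of the reply stand as limits:

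- That ratings would be missing at 70% is inferred from the reference to unconsciousness. The plan does not say so.
- The text leaves some doubt whether the resting scan itself, and not only the tasks, is repeated at each dose. The three-state comparison suggests that it is.
- The fcMRI section refers to previous publications for its methods. Whether they deal with rating periods cannot be checked here.
- No figure in the plan fixes the number, length or response mode of in-run ratings.

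A reader might infer that the artefact could pass for the whole hypothesised dose pattern, or that it undermines the powered outcome. The documents support neither. It could resemble only the rise in modularity at 70%, and path length hardly moved in the illustration. The cuff and visual sections also say nothing about resting runs, so they cannot be cited as already settling how rest is rated.

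**Conclusion.** The concern holds in a limited form. As written, the plan puts a rating task into resting runs, analyses those runs as rest with no stated handling of rating periods, and compares them across states in which the ability to rate probably differs. The exposure is mainly in seed-based and ICA connectivity, and possibly in modularity, for waking versus 70%. The analgesic contrast is not pushed toward its hypothesis, provided contamination at 35% is no greater than at waking.

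The size is unknown. The assumed settings give modularity shifts from negligible to about 1.1 SD of the run-to-run difference, and at most 0.16 SD for average path length. The conclusion assumes that the word *during* is followed literally, that volunteers at 70% do not rate, and that resting runs are acquired in each state. Severity is minor to moderate. The point should be settled before data collection, because contamination cannot be cleanly removed later if rating times were not logged.

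**What to change.** 1. **Resting runs.** In the Questionnaire section, state that resting scans contain no ratings in any state, and that intensity and unpleasantness are rated only after the resting run has ended.

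2. **Stimulus runs, separately.** Reconcile the Questionnaire section with the imaging-session and Visual Stimulation Task text. If in-run ratings are kept for cuff or visual runs, log their times and prespecify in the fcMRI section that rating periods are modelled or censored in the same way in all states.

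The cost of the first change is one sentence and the loss of any within-run ratings at rest, which is small because the post-run ratings remain. The second change need not remove the tonic-pain time course if the team wants it; it then costs a timing log and one line of analysis text. Sample size does not change.
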